### Confidentiality Statement

Data and information contained in this document are considered to constitute trade secrets and confidential commercial information, and the legal protections provided to such trade secrets and confidential information are hereby claimed under the provisions of applicable law. No part of this document may be publicly disclosed without the written consent of Philip Morris Products S.A

LS-means per randomization arm and day will be obtained (on the log-scale), as well as pairwise differences between arms per day, together with their 95%-confidence intervals and (unadjusted) p-values. Exponentiation of these quantities will lead to the geometric LS-means per randomization arm and (geometric) ratios between arms with their associated 95%-confidence intervals.

The exponentiation of the 'lsmestimate' statement above entitled 'Contrast P4M3 (CA35 and CM35 combined) vs. CIG' will allow contrasting the two P4M3 Gen 2.0 CA35 and CM35 study arms combined against the CIG arm and will be used to assess the primary study hypotheses. Similarly, the exponentiation of the two subsequent 'lsmestimate' statements will be used to assess the key secondary objectives 2 and 4 if the procedure of fixed sequence testing allows it.

For each individual BoExp in the Primary Analysis, the hypothesis will be evaluated using the 1-sided statistical test with a type I error level of 2.5% given by the 'lsmestimate' statement 'Contrast P4M3 (CA35 and CM35 combined) vs. CIG' of the model described in this section.

The study will be declared successful if the ratio of the geometric means between P4M3 (CA35 and CM35 combined) over CIG is statistically lower than 1 at Day 5 for all four Primary BoExp.

### 9.6.1.3 Supportive/Sensitivity Analyses

The model described in section 9.6.1.2 will be used to contrast all randomization arms at Days 1, 2, 3, 4, and 5. Pairwise comparisons at Days 1, 2, 3, 4, and 5 will be reported, together with their unadjusted p-values and 95%-confidence interval:

- P4M3 (CA35 and CM35 combined) vs. CIG
- SA vs. CIG
- P4M3 (CA35 and CM35 combined) vs. SA
- P4M3 CA35 vs. CIG
- P4M3 CM35 vs. CIG
- P4M3 CA35 vs. SA
- P4M3 CM35 vs. SA
- P4M3 CA35 vs. P4M3 CM35

Contrasts P4M3 CA35 vs. CIG and P4M3 CM35 vs. CIG will also be estimated one-sided with a type I error level of 2.5% through the additional 'lsmestimate' statements. These contrasts will be used to assess the key secondary objectives 2 and 4 if the procedure of fixed sequence testing (see section 9.6.3) allows.

#### Confidentiality Statement

Data and information contained in this document are considered to constitute trade secrets and confidential commercial information, and the legal protections provided to such trade secrets and confidential information are hereby claimed under the provisions of applicable law. No part of this document may be publicly disclosed without the written consent of Philip Morris Products S.A

Descriptive statistics as mentioned in section 9.1.3 for the variables of interest and associated changes from baseline will be reported by randomization study arm for the PPS and by study day. Descriptive statistics stratified by the factor described in section 9.1.1 will also be computed.

## 9.6.2 Primary Objective: Secondary Estimand Analysis

### 9.6.2.1 Secondary Estimand

This analysis refers to the secondary estimand of the primary objective. This estimand will implement the “treatment policy strategy” and reflects the intention-to-treat (ITT) principle. It will evaluate the effect of switching to P4M3 as compared to continuing to smoke CIG in the FAS rather than in the PPS. It is defined by the following components:

- Product Use Under Evaluation: This corresponds to the study arm (CIG, P4M3 CA35, P4M3 CM35, or SA) randomly allocated to subjects and is independent of whether subjects were adherent or not (FAS).
- Target Population: This is the population of adult smokers who satisfy all eligibility criteria.
- Variables of Interest: 3-HPMA, 2CyEMA, total NNAL (all expressed as concentration adjusted for creatinine in 24-hour urine), and COHb (expressed as % of saturation of hemoglobin).
- Intercurrent Events (ICEs): All ICEs will be treated as ‘treatment policy strategy’. This means that the values of the variable of interest is used regardless of whether the ICEs occur.
- Population-Level Summary Statistic: Geometric mean ratios between P4M3 (CA35 and CM35 combined) and CIG of the BoExp under consideration at Day 5

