9.5 Early Termination Procedures

When a subject is discontinued from the study, all early termination procedures listed in [Table 14](#) are performed unless the subject refuses to perform the assessments or the procedures have already been performed during that study day.

Table 14 Time Schedule – Early Termination Visit

Procedures	Additional Information
Clinical laboratory parameters (hematology, clinical chemistry) blood collection	After ≥ 6 hours of fasting, if possible - Safety panel - Pregnancy test (female only)
Urine analysis	- Safety panel
Vital signs	
ECG	
Spirometry	
Information on the risks of smoking, advice on smoking cessation and briefing on P4M3	
Concomitant medication	
Concomitant diseases	
AE/SAE recording	
P4M3 product events malfunctions/misuse	P4M3 arms only
Discharge	

Abbreviations:

AE = Adverse event; ECG = Electrocardiogram; P4M3 = e-cigarette; SAE = Serious adverse event

Confidentiality Statement

Data and information contained in this document are considered to constitute trade secrets and confidential commercial information, and the legal protections provided to such trade secrets and confidential information are hereby claimed under the provisions of applicable law. No part of this document may be publicly disclosed without the written consent of Philip Morris Products S.A

10 Quality Control and Quality Assurance

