12.5.1.3 Missing Data Strategy

In this analysis, some missing data might occur because of ICEs or because of missing samples, laboratory measurements errors, etc. The main analysis model (see section 12.5.1.4) assumes that subjects with missing data would have outcome data like

Confidentiality Statement

Data and information contained in this document are considered to constitute trade secrets and confidential commercial information, and the legal protections provided to such trade secrets and confidential information are hereby claimed under the provisions of applicable law. No part of this document may be publicly disclosed without the written consent of Philip Morris Products S.A

those in similar subjects in the same group. This type of assumption is referred to as Missing at Random (MAR). This assumption is aligned with the definition of the primary estimand.

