12.5.2.3 Missing Data Strategy

In this analysis, some missing data might occur because of missing samples, laboratory measurements errors, etc. The main analysis model (see section 12.5.2.4) assumes that subjects with missing data would have outcome data like those in similar subjects in the same group (MAR assumption). This assumption is aligned with the definition of the secondary estimand.

Confidentiality Statement

Data and information contained in this document are considered to constitute trade secrets and confidential commercial information, and the legal protections provided to such trade secrets and confidential information are hereby claimed under the provisions of applicable law. No part of this document may be publicly disclosed without the written consent of Philip Morris Products S.A.

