Appendix A Schedule of Events

	Screening	Confinement Period								Early termination ^g	Safety follow-up ^h
Visit (Time Window)		Admission ^f	Baseline	Exposure period					Discharge		3 days post Discharge
Study Day	-30 to -3	-2	-1	1	2	3	4	5	6		7 to 9
Informed consent	•										
Information on the risk of smoking; smoking cessation advice; debriefing	•	•							•	•	
Identification of current CIG brand		•									
Inclusion/exclusion criteria	•	•									
Nicotine/tobacco product use history questionnaire	•	•									
Electrocardiogram (ECG)	•		•						•	•	
Spirometry	•		•						•	•	
Demographics	•										
Medical history, concomitant diseases	•										
Concomitant disease status		•	•	•	•	•	•	•	•	•	
Prior/concomitant medication	•	•	•	•	•	•	•	•	•	•	• ⁱ
Physical examination	•										
Body height and weight ^a	•	•									
Vital signs ^b	•	•	•	•	•	•	•	•	•	•	
B: HIV, HBV and HCV	•										
B/U: Hematology, clinical chemistry, urine analysis (safety panel)	•		•						•	•	

Confidentiality Statement

Data and information contained in this document are considered to constitute trade secrets and confidential commercial information, and the legal protections provided to such trade secrets and confidential information are hereby claimed under the provisions of applicable law. No part of this document may be publicly disclosed without the written consent of Philip Morris Products S.A

	Screening	Confinement Period								Early termination ^g	Safety follow-up ^h
Visit (Time Window)		Admission ^f	Baseline	Exposure period					Discharge		3 days post Discharge
Study Day	-30 to -3	-2	-1	1	2	3	4	5	6		7 to 9
B: Pregnancy test	•	•							•	•	
U: Cotinine test	•	•									
U: Drug screen ^c	•	•									
Alcohol breath test	•	•									
P4M3 demonstration	•										
AE/SAE recording	•	•	•	•	•	•	•	•	•	•	•
Enrollment		•									
P4M3 product test ^d		•									
Randomization			•								
Informing subjects about study arm				•							
Collection of CIG butts for accountability			•	•	•	•	•	•			
E-liquid use (weight difference of Cartridges)				•	•	•	•	•			
B: BoExp in blood: COHb			•	•	•	•	•	•			
U: 24-h urine collection for BoExp (see table below)			•	•	•	•	•	•			
Intake of a caffeine tablet			•					•			
B: CYP1A2 activity			•					•			
FTND			•								
ABOUT–Product Experience			•	•	•	•	•	•			
HPT recording ^e				•	•	•	•	•			
P4M3 product events		•		•	•	•	•	•		•	

Confidentiality Statement

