#### 9.1.5 Handling of Dropouts or Missing Data

##### 9.1.5.1 Laboratory Parameters

Values outside detection limits will be substituted using the following rules (e.g., for BoExp parameters):

- Values below LLOQ will be imputed using LLOQ/2.
- Values above ULOQ will be imputed using ULOQ.

Unless otherwise stated, other missing values will not be imputed.

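### For subjects who leave, the treatment-policy (FAS) analysis becomes in effect an on-product estimate, and the FAS itself drops randomized never-users

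*SAP*

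**What the plan says.** - **Estimand.** SAP 9.6.2.1 (and Protocol 12.5.2) applies treatment policy to all intercurrent events: "This means that the values of the variable of interest is used regardless of whether the ICEs occur". The product-use component "is independent of whether subjects were adherent or not (FAS"). Study discontinuation and death are named as intercurrent events under the primary estimand (SAP 9.6.1.1).
- **Analysis.** SAP 9.6.2.2 reuses the primary MMRM on all available FAS data and reads the result as exploratory. SAP 9.1.5.1 adds: "Unless otherwise stated, other missing values will not be imputed". SAP 9.6.1.3 and 9.6.2.3 list pairwise contrasts and descriptive statistics only.
- **Missing data.** For the primary estimand, Protocol 12.5.1.3 says "some missing data might occur because of ICEs or because of missing samples, laboratory measurements errors, etc". For the secondary estimand, 12.5.2.3 says "some missing data might occur because of missing samples, laboratory measurements errors, etc", makes the same MAR assumption, and concludes: "This assumption is aligned with the definition of the secondary estimand". The SAP has no missing-data text specific to the secondary estimand.
- **Sampling after leaving.** The only blood draw in Protocol Table 14 (Section 9.5) is "Clinical laboratory parameters (hematology, clinical chemistry) blood collection", for the safety panel and pregnancy test; the rest of the visit is also safety assessments. In Appendix A, the row "B: BoExp in blood: COHb" and the 24-hour urine row have no entry under early termination.
- **Analysis set.** SAP 8.2 and Protocol 12.3.1 require at least one product use after randomization for CIG and P4M3 subjects, but not for SA subjects.
- **Who leaves.** Protocol 5.2 makes discontinuation mandatory for non-adherence. Protocol 4.1 and 6.2.3 leave it to the investigator's judgement when another tobacco or nicotine product is used.

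**The concern.** Treatment policy needs the value that occurs after the event. For a subject who leaves, that value is never measured, so the model has to supply it. Same-arm MAR supplies the value expected had the subject carried on like comparable subjects in the arm, most of whom are still on product. That suits the primary, adherent-only estimand. It does not suit one that disregards adherence, and the protocol calls the same assumption aligned with both.

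The FAS adds a second departure. A randomized CIG or P4M3 subject who stays, gives every sample and never uses product is removed because of behaviour after randomization.

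The confirmatory test is run in the PPS, so the FAS analysis is the reader's only ITT-type check on it. If the FAS estimate is pulled towards the PPS estimate by construction, their agreement says little about robustness to non-adherence.

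**Working it through.** **1. The plan's own figure.** The documents give no figure for the secondary estimand. The nearest is power for the primary objective. Allowing 15% missing, 36 × 0.85 = 30.6 → 30 and 18 × 0.85 = 15.3 → 15. SD on the log scale is √ln(1 + GCV²). The least favourable row of SAP Table 8 is 3-HPMA in the second Japanese study (GMR 52.86%, GCV 39.57%):

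- SD = √ln(1 + 0.3957²) = 0.381 and ln 0.5286 = −0.638
- noncentrality = 0.638 / (0.381 × √(1/30 + 1/15)) ≈ 5.29 on 43 df
- power at one-sided 2.5% = 99.93%

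The stated power of more than 99% reproduces.

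**2. What treatment policy would target.** The reversion rates are assumptions; the documents give none. If a share q of P4M3 subjects returns fully to CIG level, the target is GMR^(1−q).

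- 3-HPMA: 0.5286^(34/36) = 54.8% for 2 of 36; 0.5286^(31/36) = 57.8% for 5 of 36.
- 2-CyEMA (European study, GMR 13.16%, GCV 34.41%): 0.1316^(34/36) = 14.7%; 0.1316^(31/36) = 17.4%.

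**3. What the planned model returns.** Log data were simulated for four arms over five days, with 18 × 200 subjects per arm to show the large-sample limit. Within-subject correlation was 0.5 and 0.8 (assumed), with full reversion from Day 3. The model had unstructured covariance, arm by day, baseline and sex, and was fitted by maximum likelihood. Ranges cover the two correlations. Day 5 ratios for P4M3 against CIG:

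| Off-product samples kept | 3-HPMA, 2/36 | 3-HPMA, 5/36 | 2-CyEMA, 2/36 | 2-CyEMA, 5/36 |
|---|---|---|---|---|
| none | about 53% | 52.9–53.0% | 13.2% | 13.2% |
| one | 53.4–53.5% | 54.0–54.4% | 13.5–13.6% | 14.1–14.3% |
| two | 53.6–53.8% | 54.7–55.2% | not computed | 14.7–15.0% |
| all | 54.8–54.9% | 57.8–57.9% | 14.7–14.8% | 17.5% |
| **treatment-policy target** | **54.8%** | **57.8%** | **14.7%** | **17.4%** |

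The PPS gives 52.8–52.9% (3-HPMA) and 13.2% (2-CyEMA) at 5/36. With no off-product sample the FAS estimate essentially equals the PPS estimate. With full sampling it reaches the target. The gap is therefore due to the lost samples, not to the MMRM as such.

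**4. Never-users.** Suppose 1 of 18 CIG subjects abstains and falls to P4M3 level (assumption). Keeping that subject gives GMR^(17/18): 0.5286^(17/18) = 54.8% and 0.1316^(17/18) = 14.7%. Dropping the subject gives 52.9% and 13.2%, in favour of P4M3. Dropping an abstinent P4M3 never-user matters little if P4M3 is close to SA, and the direction can be the opposite.

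**5. Effect on the test.** With 15% of P4M3 subjects at CIG level, 0.5286^0.85 = 58.2%. Simulated power at 36 against 18 subjects is 99.3% for this least favourable row. At 30% the ratio is 64.0% and power is about 93%.

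**The case against.** The strongest reply is about size and standing. The FAS result is exploratory, the confirmatory test uses the PPS, and the conclusion against a ratio of 1 would very probably survive. This stands, and it limits how serious the point is.

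Reversion on the assumed scale may be rare. Cigarettes are held and dispensed by staff, butts are returned, and 5 of 36 (14%) nearly uses up the whole 15% allowance, which covers every cause of missing values. At 2 of 36 the 3-HPMA shift is about 2 points, against a 90th-percentile CI half-width of 17.8 points in SAP Table 8. The figures are illustrations, not forecasts.

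Never-users should also be few. Subjects unwilling to use P4M3 leave before randomization, all smoke at least 10 cigarettes a day, and a single use keeps a subject in the FAS. However, Protocol 12.1.2 provides for abstinence in the product arms (in a safety-analysis definition), 6.2 does not force use, and 4.1 keeps quitters in the study. The wording conflict is real even if the count is zero.

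Omitting intercurrent events in 12.5.2.3 is partly right, because values after a positive COVID test are kept under treatment policy. It is not right for discontinuation.

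Leavers who adhered until they left are in the PPS too. Both analyses then treat them under the same MAR assumption, so agreement on them is built in.

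Finally, imputing from the CIG arm is one-directional, and it does not deal with death. Both are true; the analysis should be labelled accordingly.

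**Conclusion.** The concern holds. For subjects who leave, the analysis labelled treatment policy estimates something close to continued adherence. The alignment statement in Protocol 12.5.2.3 is wrong for discontinuation, no analysis departing from MAR is planned, and the FAS definition contradicts the estimand it is meant to serve.

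Subjects who stay and are sampled are handled correctly in the FAS once they have used product. This includes mis-randomized subjects, protocol deviators and those sampled after a positive COVID test.

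Under full reversion from Day 3 in 2 to 5 of 36 P4M3 subjects, with no off-product sample, the FAS ratio is too favourable by about 2 to 5 percentage points for 3-HPMA and 1.5 to 4 for 2-CyEMA. With one or two off-product samples the gap is smaller. The logic is certain; the size depends on an unknown number of leavers and on how far they revert. What is at stake is the reported size of the reduction and the apparent FAS/PPS agreement, not the test against 1. It should be corrected, but it does not undermine the primary analysis.

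**What to change.** 1. **FAS (SAP 8.2, Protocol 12.3.1).** Remove the product-use condition and place it in the PPS definition (SAP 8.3). The PPS, and so the confirmatory analysis, is unchanged.
2. **Analysis (SAP 9.6.2).** Keep the planned MMRM with all observed values as the main FAS analysis. Report per arm how many FAS subjects lack a Day 5 value because of an intercurrent event. Add one labelled non-MAR sensitivity analysis for subjects whose biomarkers stop at or after discontinuation or non-adherence. One option is reference-based multiple imputation from the CIG arm, given baseline and sex, for CA35, CM35 and SA leavers. CIG leavers are already predicted from their own arm under MAR.
3. **Wording.** Correct Protocol 12.5.2.3, or override it in SAP 9.6.2 and list the change in SAP 7. Name discontinuation after an intercurrent event as a cause of missing data, and say that for leavers MAR represents continued adherence and is not aligned with treatment policy.
4. **Consistency.** Reconcile the mandatory wording in Protocol 5.2 with the discretionary wording in 4.1 and 6.2.3, since this determines how many subjects have samples after the event.

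The cost is one imputation program, one count table and text changes; no new data are needed. The sensitivity ratios will be slightly less favourable and slightly wider, and imputation from the CIG arm is deliberately conservative for subjects who leave for other reasons, such as an adverse event.

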### 9.6.2.2 Main Analysis

This analysis will be conducted using the same model as the one described in section 9.6.1.2, except that it will use the FAS instead of the PPS and all available data will be included in the model.

In section 9.6.1.2, the criterion to declare the study successful was provided. Here, the same difference will be computed and interpreted exploratorily using the same type I error level as for the primary confirmatory hypothesis.

### 9.6.2.3 Supplementary Analysis

Randomized study arms will be contrasted at Days 1, 2, 3, 4, and 5. Pairwise comparisons at Days 1, 2, 3, 4, and 5 will be reported, together with their unadjusted p-values and 95%-confidence interval:

- P4M3 (CA35 and CM35 combined) vs. CIG
- SA vs. CIG
- P4M3 (CA35 and CM35 combined) vs. SA
- P4M3 CA35 vs. CIG
- P4M3 CM35 vs. CIG
- P4M3 CA35 vs. SA
- P4M3 CM35 vs. SA
- P4M3 CA35 vs. P4M3 CM35

As in the primary estimand analysis, the contrasts P4M3 CA35 vs. CIG and P4M3 CM35 vs. CIG will also be estimated one-sided with a type I error level of 2.5% through the additional ‘lsmestimate’ statements provided in section 9.6.1.2. These contrasts will be used exploratorily to assess the key secondary objectives 2 and 4 if the procedure of fixed sequence testing allows.

Descriptive statistics as mentioned in section 9.1.3 for the variables of interest and associated changes from baseline will be reported by randomization study arm for the FAS and by study day. Descriptive statistics stratified by the factor described in section 9.1.1 will also be computed.

## 9.6.3 Secondary Objective Analyses

### 9.6.3.1 Key Secondary Objectives

The 1st key secondary objective of the study is to demonstrate the reduction of Secondary BoExps to selected HPHC in smokers who switch from CIGs to P4M3 use compared to those who continue to smoke CIG. The analyses used for the primary and secondary estimands will be repeated with the Secondary BoExp endpoints.

Subsequent key secondary objectives (from 2 to 5) will use the statistical models developed to assess the primary and 1st key secondary objectives, except that they will contrast either CA35 vs. CIG or CM35 vs. CIG (instead of CA35 and CM35 combined vs. CIG).

The evaluation of the key secondary objectives will be done using a procedure of fixed sequence testing as specified in Figure 2. This first key secondary objective will only be tested

#### Confidentiality Statement

[figure not shown]
---

Data and information contained in this document are considered to constitute trade secrets and confidential commercial information, and the legal protections provided to such trade secrets and confidential information are hereby claimed under the provisions of applicable law. No part of this document may be publicly disclosed without the written consent of Philip Morris Products S.A.

---

if the primary objective is demonstrated, which preserves the study-wise type I error rate at the 2.5%. An additional benefit will be declared if the ratio of the geometric means between P4M3 (CA35 and CM35 combined) over CIG is statistically lower than 1 at day 5 for all four additional key secondary BoExp.

If both the primary and first key secondary objectives are successful, then the 2nd key secondary objective will be tested with type I error level of 2.5%, and similarly in sequence until objective 6 (Figure 2). If, during subsequent tests, any of the objectives are not successful, the sequence testing will stop, and further testing will cease. Specifically, if the hypothesis for a single BoExp is rejected, then the fixed sequence testing will stop.

**Figure 2 Representation of the Procedure of Fixed Sequence Testing**

### 9.6.3.2 Secondary Objective

The secondary objective of this study is to monitor safety and tolerability in all subjects during the study. All safety analyses will be conducted with the SAF (inferential analyses will not be performed on safety endpoints) and are described in 9.6.5.

